#### 4.1.3. Intercurrent Events Strategies

For the primary and key secondary estimands analysis, the following ICEs should be considered:

- Treatment discontinuation due to lack of efficacy or an AE; and any other reasons including study treatment noncompliance.
- Additional/alternative therapies used after the first dose of study intervention including PRN use of PD medications, switching PD treatments, or any dose/regimen change of background PD treatments.

The ICEs will be handled using 2 approaches:

[figure not shown]
- For the main analytical approach, the treatment policy strategy will be used to address all defined ICEs. The treatment policy strategy is defined as the effect of the randomized intervention over the study period regardless of the occurrence of an intercurrent event. Per the treatment policy, data should be collected after the occurrence of intercurrent event and will be included for statistical analyses and data interpretation.
- For the supplemental analysis approach, hypothetical strategy will be used to address post-ICE observations up to Week 17 due to discontinuation of study treatment. For ICEs of additional/alternative therapies used after the first dose of study treatment, treatment policy should still be applied. The hypothetical strategy is defined as the pharmacologic effect of JZP385 compared to placebo assuming the intercurrent event did not happen with continuation of randomized treatments for the duration of the study. Analysis will be conducted using data collected at time points that are obtained at or prior to participants discontinuing from study treatment and combined with modeled values for post-discontinuation timepoints where the underlying assumptions are considered as appropriate.

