9.4.1.3. Intercurrent Event Strategies

For the primary and key secondary estimands, the following ICEs should be considered:

- Treatment discontinuation due to lack of efficacy or AE; and any other reason including study intervention noncompliance, and other significant protocol deviations.
- Additional/alternative therapies including PRN use of medications to treat tremor, changing background PD treatments, and switching PD treatments.

The ICEs will be handled using 2 approaches:

- As the main approach, treatment policy will be used to address the ICEs. Treatment policy is defined as the effect of the randomized treatment over the study period regardless of whether randomized treatment is continued. Per the treatment policy, data collected (during Efficacy Follow-up Visits) after participants experience a treatment discontinuation ICE will be included for analysis.
- As a supplemental approach, additional analyses of the primary and key secondary estimands will use the hypothetical strategy to address the ICEs. This strategy is defined as the pharmacologic effect of suvecaltamide compared to placebo assuming the intercurrent event did not happen with continuation of randomized treatments for the duration of the study. Analyses will be conducted using data collected at time points that are obtained at or prior to participants discontinuing from randomized treatment and combined with modeled values for post-discontinuation timepoints where the underlying assumptions are considered as appropriate.

In summary, ICEs will be addressed using the treatment policy estimand for the main analysis of the primary and key secondary endpoints and using the hypothetical strategy estimand for supplemental analyses.

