9.4.2. Primary Estimand

The attributes of the primary estimand are listed in [Section 3](#).

For the main estimator analysis, a MMRM will be used to include the change in the TETRAS composite outcome score from Baseline to Weeks 5, 9, 13, and 17. The model will include treatment group, visit, treatment-by-visit interaction, baseline-by-visit interaction, and randomization stratum as fixed effects; baseline TETRAS composite outcome scores as a covariate; and week repeated within each participant as repeated effect. An unstructured variance-covariance matrix will be used to model the correlation among repeated measurements. The Kenward-Roger adjustment of degrees of freedom along with REML will be used to make proper statistical inference. Within-group LS means and the associated 2-sided 95% CIs, treatment difference in LS means and associated 2-sided 95% CIs and p-values will be reported.

Per the treatment policy, the main analyses will include data collected during the Efficacy Follow-up Visits for participants who experience ICEs. However, for participants who experience ICEs and do not attend Efficacy Follow-up Visit(s), missing data will be handled per [Section 9.4.1.5](#).

For sensitivity analysis, control-based imputation methods ([Roger, 2012](#)) will be used to handle missing observations in addition to treatment policy. Details will be further defined in SAP.

For supplementary analysis, a hypothetical strategy will be used to include data points up to the timepoint when a participant experiences an ICE into the MMRM specified above. This will serve as complementary analysis and will ignore observations collected after an ICE.

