#### **4.9. Changes to the Protocol-Planned Analyses**

This SAP added the definition of FAS, defined as “The Full Analysis Set includes all participants who are randomized.” This analysis set will be the primary analysis set for all efficacy analyses.

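### The SAP's hypothetical supplemental analyses keep values recorded after added or changed therapy, which Protocol 9.4.2 and 9.4.3.1 would drop, and SAP 4.9 does not declare the change

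*SAP*

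**What the plan says.** Protocol 9.4.1.3 names two kinds of ICE. One is treatment discontinuation. The other is "Additional/alternative therapies including PRN use of medications to treat tremor, changing background PD treatments, and switching PD treatments". The main approach to both is treatment policy. As a supplement, "additional analyses of the primary and key secondary estimands will use the hypothetical strategy to address the ICEs", with no exception for either kind. It explains the strategy thus: "This strategy is defined as the pharmacologic effect of suvecaltamide compared to placebo assuming the intercurrent event did not happen". The endpoint sections then give the data rule. Protocol 9.4.2 takes TETRAS composite data up to the ICE into the MMRM and "will ignore observations collected after an ICE". Protocol 9.4.3.1 has the same rule for CGI-S response and imputes the removed values by 2-step MI.

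SAP 4.1.3 lists the same two kinds of ICE but confines the hypothetical strategy to discontinuation of study treatment. For the other kind it says: "For ICEs of additional/alternative therapies used after the first dose of study treatment, treatment policy should still be applied". SAP 4.2.5 and 4.3.5 follow this and set only post-discontinuation values to missing. The SAP keeps the protocol's description of the target as a pharmacologic effect. SAP 1 says that changes to the protocol-planned analyses are described in 4.9, and the only entry there begins "This SAP added the definition of FAS".

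**The concern.** A participant who stays on study drug but starts, switches or re-doses another treatment has Week 17 values that reflect both treatments. The protocol's supplementary analysis was meant to set such values aside and estimate what the study drug does without them. Under the SAP they stay in, so the supplement answers a different question from the one the protocol posed. A reader who checks 4.9 would not learn this and could take the reported supplement for the protocol's any-ICE analysis. What is at stake is the interpretation of the primary and key secondary results, not the test of either.

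**Working it through.** **Step 1: the rules side by side.**

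| Item | Protocol | SAP |
|---|---|---|
| Kinds of ICE | 9.4.1.3: discontinuation; additional/alternative therapy | 4.1.3: the same two |
| Scope of hypothetical strategy | 9.4.1.3: both kinds | 4.1.3: discontinuation only |
| General data sentence | 9.4.1.3: cut at discontinuation | 4.1.3: cut at discontinuation |
| TETRAS composite | 9.4.2: drop values after an ICE, MMRM | 4.2.5: drop values after discontinuation, MMRM |
| CGI-S response | 9.4.3.1: drop values after an ICE, 2-step MI | 4.3.5: drop values after discontinuation, MI |
| Declared as a change | – | 4.9: no |

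Take a participant who completes study drug and changes background PD treatment between Weeks 9 and 13. Under Protocol 9.4.2 and 9.4.3.1 the Week 13 and 17 values are removed. Under SAP 4.2.5 and 4.3.5 they are used.

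**Step 2: does another planned analysis remove these values?** The main analyses (SAP 4.2.2, 4.3.2) are treatment policy. The control-based imputation and tipping-point analyses of the composite (4.2.4) are run under treatment policy. The CGI-S sensitivity analyses (4.3.4) alter only missing values. The supplemental analyses (4.2.5, 4.3.5) keep values after added therapy. That leaves the subgroups in 4.2.3 and 4.3.3 by change of concomitant PD medication and by prohibited medication after baseline. The participants without such an event contribute no values after it, but each subgroup handles one type of event, membership is decided after randomisation, and sparse results may be withheld.

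**Step 3: the plan's own figures, for scale.** SAP 5 has 64 evaluable per arm, difference 3.0, SD 6.0, two-sided 0.05, t-test. With the noncentral t distribution, 63 per arm gives 79.5% power and 64 gives 80.1%, so 64 is reproduced. Then 64 / (1 − 0.20) = 80 per arm, 160 in total. The standard error of the difference is 6.0 × √(2/64) = 1.06 points.

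**Step 4: illustration of the shift.** The documents give neither the frequency of added therapy nor the gain from it, so both are assumptions. If shares p_P (placebo) and p_A (active) add or change therapy and each such participant gains e points at Week 17, equally in both arms, the expected difference is

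D = 3.0 − (p_P − p_A) × e.

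| Placebo v active use | e = 2 | e = 4 | e = 6 |
|---|---|---|---|
| Equal | 3.0 | 3.0 | 3.0 |
| 10% v 5% | 2.9 | 2.8 | 2.7 |
| 15% v 5%, or 20% v 10% | 2.8 | 2.6 | 2.4 |
| 25% v 5% | 2.6 | 2.2 | 1.8 |
| 5% v 10% | 3.1 | 3.2 | 3.3 |

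For example, 10% v 5% with e = 2 gives 3.0 − 0.05 × 2 = 2.9. A shift of 0.4 points is 0.4 / 1.06 = 0.38 of a standard error. The extreme 25% v 5% case with e = 6 shifts the difference by 1.2 points, or 1.13 standard errors.

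For CGI-S the same algebra applies to proportions, with e replaced by the share c of users who become responders because of the added therapy. With c equal in both arms, 10% v 5% use shifts the planned 25-point difference (65% v 40%) by at most 0.05 × 1 = 5 percentage points.

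**The case against.** The best defence is that the SAP is open about what it does. SAP 4.1.3 assigns treatment policy to added therapy in plain words just before it defines the hypothetical strategy, and 4.2.5 and 4.3.5 limit the counterfactual to discontinuation. A mixed strategy of this kind, the effect had nobody discontinued and regardless of added therapy, can be a coherent estimand. The SAP also has some support in the protocol, because the data sentence in Protocol 9.4.1.3 itself cuts only at discontinuation. All of this stands. It does not remove the difference from 9.4.2 and 9.4.3.1, which set the rule for each endpoint, or the silence of 4.9.

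Three stronger readings are tempting and are not supported.

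- A reader might infer that the SAP's analysis is invalid or estimates nothing meaningful. It estimates the mixed quantity; the pharmacologic-effect label is loose.
- A reader might infer that the plan ignores added therapy, or that the bias must run against the drug. The subgroups in 4.2.3 and 4.3.3 partly examine it, and Step 4 shows that the sign depends on which arm uses more. The protocol also requires stable PD medication throughout (inclusion criterion 5 and 6.8), which should limit such events.
- A reader might infer that the SAP's wider wording, PRN use of PD medications where the protocol has PRN use of medications to treat tremor, already distorts results. Under the SAP that ICE is handled by treatment policy everywhere, so the wording does not change which values these analyses use. It would matter only once the ICE triggers removal of data.

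It is also fair to say that removing observed values and relying on MAR has its own weakness. That is a reason to add the protocol's version and not to replace the SAP's outright.

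**Conclusion.** The documents conflict for both endpoints in the testing sequence. The protocol's any-ICE supplementary analysis is not in the SAP, its replacement is not declared, and no other planned estimand analysis removes the effect of added or changed therapy. The consequence is limited to supplemental analyses outside the testing sequence.

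The numerical effect cannot be determined from the documents. It is about zero if use and gain are balanced, a shrinkage if placebo participants use more, and an inflation if active participants use more. The illustrated range, from 1.8 to 3.3 points against a target of 3.0, rests wholly on assumed rates and gains. At 10% v 5% use the shift is 0.1 to 0.3 points, less than a third of the planned standard error. It is worth correcting because the protocol promised this estimate and restoring it is cheap.

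**What to change.** 1. In SAP 4.1.3, 4.2.5 and 4.3.5, keep the discontinuation-only version if it is wanted, but label it as the effect without discontinuation regardless of added therapy. List it in 4.9 as a departure from Protocol 9.4.2 and 9.4.3.1.
2. Add the protocol's any-ICE version for both endpoints. Set to missing all values after the first of treatment discontinuation or additional/alternative therapy, then use the existing MMRM for the TETRAS composite and the existing 2-step MI with the CMH test for CGI-S response.
3. For that version, define the therapy ICE in the protocol's terms ("Additional/alternative therapies including PRN use of medications to treat tremor", with changed or switched PD treatment). The SAP's wider PRN wording would also remove values after PRN dopaminergic use for non-tremor symptoms, which exclusion criterion 19 permits.

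The cost is a short SAP edit and one more run of existing models. The added analysis will have more missing data. It will also rely on MAR for participants who may have added therapy because their tremor was uncontrolled, and the report should say so beside the result.

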#### 4.1.4. Treatment Dropouts and Missing Observations Handling

Although this study includes Efficacy Follow-up visits at Weeks 9, 13, and 17 to follow up with participants who discontinue the study intervention early, missing data caused by reasons defined outside the scope of intercurrent events can still occur (e.g., intermittent missing data due to noncompliance). In that case, the MAR assumption will be considered appropriate and missing data will be handled accordingly by MMRM or MI.

Figure 2 below depicts how missing data due to early discontinuation will be addressed under the main analytical approach of the primary and key secondary efficacy estimands.

**Figure 2: Management of Missing Data due to Early Discontinuation for the Primary and Key Secondary Efficacy Estimands**

Under the main analytical approach, missing data will be assumed to be MAR for participants who do not complete the Efficacy Follow-up visit(s). The MMRM (for the TETRAS composite outcome score) and MI (for CGI-S response) assume participants with missing data would have efficacy outcomes similar to those participants in their respective study intervention group, randomization stratum, and initial trajectory who completed the study. The MMRM produces an estimate of the treatment effect via restricted maximum likelihood estimation, and a 2-step MI method produces a group of statistical estimates and will be pooled using Rubin's rule.

Under the sensitivity analyses, control-based imputations (for TETRAS composite outcome score) and NRI (for CGI-S response) will be used to treat missing data among participants discontinued due to an adverse event or lack of efficacy. Tipping-point analyses will be further conducted to assess the robustness of the underlying MAR assumption used in MMRM and MI.

## 4.2. Primary Estimand Analysis

### 4.2.1. Definition of Primary Estimand

The attributes of the primary estimand are listed under Section 1.1.

TETRAS composite outcome score is the sum of modified items 1 to 11 of the TETRAS-ADL and modified items 6 (6a and 6b) and 7 of the TETRAS-PS, which ranges from 0 to 42. Higher scores indicate more functional and performance-based impairment due to tremor symptoms.

The scoring for each item of the TETRAS-ADL subscale will be modified from 5 response options to 4 as follows:

- A score of 0 or 1 will be modified to a score of 0
- A score of 2 will be modified to a score of 1
- A score of 3 will be modified to a score of 2
- A score of 4 will be modified to a score of 3
- A missing score will remain missing

The scoring of each item of the TETRAS-PS subscale will be modified from 9 response options to 4 as follows:

- A score of 0, 0.5, or 1 will be modified to a score of 0
- A score of 1.5 or 2 will be modified to a score of 1
- A score of 2.5 or 3 will be modified to a score of 2
- A score of 3.5 or 4 will be modified to a score of 3
- A missing score will remain missing

### 4.2.2. Main Analytical Approach

The analysis will be conducted under the treatment policy framework using the Full Analysis Set.

For the main estimator analysis, a MMRM specified below will be used to analyze the change of the TETRAS composite outcome score from Baseline to Weeks 5, 9, 13 and 17.

$$dTCOM_{ij} = \alpha_{j(i)} + \beta_1 * baseTCOM_i + \beta_2 * week_j + \beta_3 * treatment_i + \beta_4 * treatment_i * week_j + \beta_5 * baseTCOM_i * week_j + \beta_6 * stratum_i + \varepsilon_{ij}$$

The model will include treatment group ( $treatment_i$ ), study visit ( $week_j$ ), treatment-by-visit interaction ( $treatment_i * week_j$ ), baseline-by-visit interaction ( $baseTCOM_i * week_j$ ), and randomization stratum ( $stratum_i$ ) as fixed effects, baseline TETRAS composite outcome score ( $baseTCOM_i$ ) as a covariate, and week repeated within each participant as repeated effect ( $\alpha_{j(i)}$ ).

An unstructured variance-covariance matrix will be used to model the correlation among repeated measures. If the model fails to converge on the Newton-Raphson Algorithm, the alternative Fisher scoring algorithm should be explored before considering other variance-covariance structures.

The Kenward-Roger's adjustment of degrees of freedom along with restricted maximum-likelihood (REML) computation method will be used. Least square mean (LS mean) and standard error (SE) at Weeks 9, 13 and 17 will be provided and graphed in a line plot for both treatment groups. The LS mean difference between JZP385 and placebo at Weeks 9, 13 and 17, along with the 2-sided 95% confidence interval (CI) and associated p-value will be provided.

Treatment dropouts and missing observations for the main analytic approach will be handled according to Section 4.1.4.

An example SAS code for MMRM analysis is as follows:

```
PROC MIXED DATA=INDATA METHOD=REML;
```

```
CLASS SUBJECT TRT WEEK STRATUM;
MODEL CHG = BASELINE TRT WEEK STRATUM TRT*WEEK BASELINE*WEEK /
RESIDUAL OUTP=RESIDUAL DDFM=KR;
REPEATED WEEK/TYPE=UN SUB=SUBJECT;
LSMEANS TRT*WEEK / CL DIFF ALPHA=0.05;
RUN;
```

#### 4.2.3. Subgroup Analyses

Analyses on subgroups identified below for the primary estimand will be conducted following the main analytical approach (except for subgroup on randomization stratum), under the treatment policy framework and using the Full Analysis Set.

- Sex at birth (Female, Male)
- Region (North America, Europe)
- Randomization stratum: TETRAS composite outcome score ( $\leq 17$ ,  $> 17$ )
- Age ( $< 65$ ,  $\geq 65$ ) Family history of PD (No, Yes)
- Change of concomitant PD medications (No, Yes)
- Use of any prohibited medications after Baseline (No, Yes)
- Presence of On and Off periods (No, Yes)
- Race (White, Not White)

For subgroup analysis on randomization stratum, MMRM will adapt from the main analytical approach to exclude the randomization stratum.

It should be noted that the study was not designed to detect treatment differences while preserving adequate statistical power within any subgroups. Thus, estimation on the treatment difference within subgroups will not be provided (LS means, standard error, LS Mean Difference (95% CI) and p-value) if the data are too sparse. A forest plot summarizing the treatment difference and 95% CI will be provided for each subgroup with sufficient sample size.

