5.1. Inclusion Criteria

Participants are eligible to be included in the study only if all of the following criteria apply:

1. Male and female participants ages 40 to 85 years inclusive, at time of signing the ICF.
2. Body mass index from 17 to 45 kg/m² (inclusive) at Screening.
3. Diagnosis of clinically probable or clinically established PD meeting the MDS 2015 criteria ([Postuma, 2015](#)).
4. Participants must be individually optimized on PD medications for the treatment of other cardinal signs of PD (bradykinesia, rigidity) per the judgement of the investigator.
Optimized treatment is defined as the maximum therapeutic effect obtained with PD medications when no further improvement is expected regardless of any additional adjustments to these medications or when the PD medications or adjustments to these medications are anticipated to result in intolerable side effects. This will be based on the investigator's clinical judgement.
5. Participants must be on a stable dosing regimen of their permitted PD and/or other tremor (eg, propranolol) medications for the treatment of motor symptoms for at least 6 weeks prior to Screening and do not anticipate the need to make any changes for the duration of the study. A lack of use of medications used to treat motor symptoms also must be stable for 6 weeks prior to Screening and remain stable for the duration of the study (eg, participants who tried PD medications and are no longer taking them must be off of these medications and stable for 6 weeks prior to Screening).
6. For participants who experience motor fluctuations, tremor must also be present during "ON" periods and participants should be able to have tremor symptoms evaluated during "ON" periods, as determined by the investigator, in relation to the participant's PD medications. If necessary, participants may take their PD medications in the clinic during visits where tremor symptoms are evaluated (timing of PD medications relative to tremor evaluations can be determined by the investigator).
7. Participants have moderate to severe impairment associated with tremor at both the Screening and Baseline Visits, as determined by all the following:
 - a. A score of > 21 on the TETRAS-ADL subscale; and
 - b. This criterion has been removed.
 - c. CGI-S rating of tremor severity of > 2 (at least moderate for participants ability to function).

8. Contraception:

a. Male participants:

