6.8. Concomitant Therapy

Any medication or vaccine (including over-the-counter or prescription medicines, recreational drugs, vitamins, and/or herbal supplements) that the participant is receiving at the time of enrollment or receives during the study must be recorded along with:

- Reason for use;
- Dates of administration including start and end dates; and
- Dosage information including dose and frequency.

Concomitant treatment with certain medications/therapies is not permitted during the study (see [Section 5.2](#)).

Participants will continue their permitted PD medication(s) at the same stable dose(s) and regimen(s) as in the 6 weeks immediately prior to the study and will remain on the same dose(s) and regimen(s) of these medication(s) until the end of the study. On clinic visit days, site staff will record the time of the last dose(s) of PD medication(s) prior to the efficacy assessments. For all participants, efficacy assessments should occur during “ON” periods, as determined by the investigator, in relation to the participant’s PD medication(s).

Refer to the permitted, prohibited, and cautionary list of medications in the Trial Site Binder.

The Medical Monitor should be contacted if there are any questions regarding concomitant or prior therapy.

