### 4.3.3. Subgroup Analyses

Analyses on subgroups identified below for the key secondary estimand will be conducted following the analysis method in main analytical approach (except for subgroup on randomization stratum), under the treatment policy framework and using the Full Analysis Set.

- Sex at birth (Female, Male)
- Region (North America, Europe)
- Randomization stratum: TETRAS composite outcome score ( $\leq 17$ ,  $> 17$ )
- Age ( $< 65$ ,  $\geq 65$ )
- Family history of PD (No, Yes)
- Change of concomitant PD medications (No, Yes)
- Use of any prohibited medications after Baseline (No, Yes)
- Presence of On and Off period (No, Yes)
- Race (White, Not White)

For subgroup analysis performed on randomization stratum, MMRM will adapt from the main analytical approach to exclude the randomization stratum.

It should be noted that the study was not designed to detect treatment differences with high statistical power within any subgroups. Thus, estimation on the treatment difference on CGI-S response within subgroups will not be provided (adjusted difference, unadjusted difference, 95% CI based on stratified Newcombe method and p-value) if the data are too sparse. A forest plot summarizing the adjusted treatment difference on CGI-S response and 95% CI will be provided for each subgroup with sufficient sample size.

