#### **4.7.6. Prior and Concomitant Medications**

##### **Derivations and Definitions:**

Prior and concomitant medications will be coded to ATC level 4 and preferred drug name using WHO Drug Dictionary Version March 2024, and will be classified as follows:

Prior medication is defined as any medication started prior to the first dose of study treatment.

Concomitant medication is defined as any medication started prior to the first dose of study intervention and continued beyond the first dose of study treatment, or any medication started on or after the first dose of study treatment up to the last dose of study treatment.

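### SAP 4.2.3 and 4.3.3 place one post-randomisation factor, and one that very probably is, among the baseline subgroups; treatment differences within their levels are not randomised comparisons

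*SAP*

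**What the plan says.** SAP 4.2.3 (primary estimand) and 4.3.3 (key secondary estimand) each list the subgroups to be analysed by the main method in the Full Analysis Set. Most are fixed at entry: sex, region, randomisation stratum, age, family history, race. Two are of another kind: "Use of any prohibited medications after Baseline (No, Yes") and "Change of concomitant PD medications (No, Yes").

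Every subgroup level receives a treatment difference with 95% CI and p-value, and a forest-plot row where numbers suffice. Estimates are withheld if data are too sparse; no threshold is given. The only caution in 4.2.3 is that "the study was not designed to detect treatment differences while preserving adequate statistical power within any subgroups". In 4.3.3 it is that "the study was not designed to detect treatment differences with high statistical power within any subgroups". Neither section says that some factors arise after randomisation.

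**The concern.** A subgroup comparison keeps the protection of randomisation only if membership is settled before treatment can act on it. Use of a prohibited medication, or a change of PD medication, can be a consequence of how the participant fares on the assigned arm. Placebo participants who stayed off other therapy and active participants who stayed off it may then be differently selected, and the same holds for those who did not.

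Two misreadings follow easily. A gap between the Yes and No rows looks like effect modification. The No row looks like the effect in people without other therapy. Neither reading is supported, and the rows would stand in the same forest plot as valid baseline subgroups with no interpretive caution.

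**Working it through.** **Timing of the two factors.**

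- *Prohibited medication.* SAP 1.2.1 places randomisation at Baseline, and the factor counts use after Baseline. No inference is needed.
- *PD-medication change.* The factor has no time reference, so its timing must be inferred:
  - Protocol 5.1, criterion 5, requires a stable regimen for at least 6 weeks before Screening from participants who "do not anticipate the need to make any changes for the duration of the study".
  - Protocol 6.8 says participants "will remain on the same dose(s) and regimen(s) of these medication(s) until the end of the study".
  - SAP 4.1.3 counts as intercurrent events "therapies used after the first dose of study intervention including PRN use of PD medications, switching PD treatments, or any dose/regimen change" of background PD treatment.
  - SAP 4.7.6 calls a medication concomitant if it continued past the first dose or is "any medication started on or after the first dose of study treatment up to the last dose of study treatment".

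Together these make a post-dose meaning very probable. A change between Screening and Baseline is not strictly excluded.

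**Design inputs (SAP 5).** Difference 3.0, SD 6.0, two-sided 0.05, t-test: 64 per group gives 80.1% power by the noncentral t distribution (63 gives 79.5%), and 64 / 0.8 = 80 per group, 160 in total. For CGI-S, 65% against 40% with 64 per group gives 81.6%. The stated figures reproduce and are not in question.

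**What a row estimates.** With S = 1 for Yes and Y the Week 17 change, the No row is E[Y | placebo, S = 0] − E[Y | active, S = 0]. It equals the treatment effect in a common population only if the arms are comparable given S = 0.

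**Illustration.** The documents give no usage rates and no link between use and response, so everything except 3.0, 6.0, 64 per arm and the CGI-S rates is assumed:

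- Changes at Weeks 13 and 17 are bivariate normal, SD 6, correlation 0.6 or 0.8.
- The true difference is 3.0 for everyone (placebo minus active), with no interaction.
- logit P(S = 1) = a + b × (Week 13 score in SD units), with a set so that placebo use is 5%, 10%, 20% or 30%.
- 2,000,000 simulated participants per arm per scenario.

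*Same link in both arms (true value 3.0):*

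| b per SD | No row | Yes row |
|---|---|---|
| 0.5 | 2.89 to 2.98 | 2.88 to 2.97 |
| 1.0 | 2.70 to 2.94 | 2.62 to 2.93 |
| 1.5 | 2.51 to 2.90 | 2.30 to 2.63 |

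The largest No-row bias is 3.0 − 2.51 = 0.49, against a row SE of 1.06 to 1.24. The two rows differ by at most 0.33, so almost no false interaction appears. For CGI-S (true difference 25 points) the No row shows 21.6 to 24.8. If use is unrelated to outcome, the bias is zero.

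*Link on placebo only, 20% to 30% use:*

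| b per SD | No row | Yes row |
|---|---|---|
| 0.5 | 2.3 to 2.7 | 4.2 to 4.8 |
| 1.0 | 1.8 to 2.4 | 5.1 to 6.3 |

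The Yes level then has 64 × 0.20 = 12.8 to 64 × 0.30 = 19.2 participants per arm. Its SE is roughly 6 × √(2 / 12.8) = 2.4 down to 6 × √(2 / 19.2) = 1.9; the within-level SD is slightly below 6, so the simulation gives 2.3 to 1.9. At b = 1.0 the gap between rows is 3.0 to 4.1, or 1.2 to 1.8 of its own SE. At b = 1.5 the Yes row reaches about 7.4 at 20% use and about 9 at 5% use. The slope chosen sets the result.

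*No treatment effect at all* (Week 9 driver, correlation 0.7, b = 1.0). If treatment itself shifts the log-odds of Yes by −1, the false differences, placebo minus active, are −0.5 (Yes) and −0.3 (No). If it shifts them by +1, they are +0.7 and +0.6. The sign is not predictable either.

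**The case against.** The strongest reply is that these rows carry no claim. Only two hypotheses are tested (SAP 2 and 2.1), no interaction test is planned, and the SAP nowhere says that the rows show effect modification. Both sections disclaim power and withhold sparse estimates. Under the plainest assumption, the same link in both arms, the bias is below the row's standard error; large distortion needs an arm-specific link that no document supports. The prohibited-medication factor shows its timing in its name. A sponsor may also legitimately want to see outcomes by these events.

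Most of this stands, and it sets the weight of the point. It does not remove the point. A power caution tells the reader that the row is imprecise, not that it compares selected groups. Naming the timing is not the same as saying how the row may be read, and the second factor does not name it. The wish to see outcomes by event can be met by a separate descriptive display.

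A reader might infer more than the documents allow:

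- *That the primary or key secondary result is compromised.* It is not. The main analyses include participants regardless of these events under treatment policy and do not condition on them.
- *That both factors are proven to be post-randomisation.* Only the first is. The second is a strong inference from a definition that is missing.
- *That a large or one-directional bias is expected.* Nothing in the documents fixes its size or sign.

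**Conclusion.** The point holds on validity, not on a predicted bias. One listed factor is post-randomisation by its wording, and the other very probably is. Within-level differences, intervals and p-values for these factors are not randomised comparisons.

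Under the assumed scenarios the distortion ranges from zero, through less than one row SE (same link in both arms), to several points in small Yes groups (placebo-only link). The upper end reflects the assumed slope rather than anything in the plan. No stated figure and neither confirmatory test changes. The proportionate label is a free improvement: worth making before database lock, with no bearing on the trial's main conclusions.

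**What to change.** Remove both factors from the subgroup lists and forest plots in SAP 4.2.3 and 4.3.3, and add wording such as:

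> Change of concomitant PD medications and use of prohibited medications, from first dose to Week 17, will be summarised by randomised arm (number and percent) in the Full Analysis Set, labelled as post-randomisation events. They are not subgroup factors. Any display of outcome by these events will be separate from the subgroup results, descriptive and without p-values, and will state that the arms within a level may differ through selection.

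If the PD-medication factor is meant as a change before randomisation, define it with that cut-off; it may then stay.

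The cost is SAP wording only: two fewer subgroup factors per endpoint and no new model. The counts are partly planned already, since SAP 4.7.6 summarises concomitant PD medications and SAP 4.7.3 summarises protocol deviations, both in the Full Analysis Set.
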